Off-pump CABG is performed to improve cardiac blood flow without the use of a cardiopulmonary bypass machine which may provoke complications including stroke, renal failure, and blood loss. Despite potential benefits, off-pump surgery can cause complications including graft occlusion, myocardial infarction, and neurocognitive deficits. The prevalence of such complications varies widely in the literature, with some studies suggesting it ranges from 5% to 30%, influenced by patient comorbidities and surgical technique. Continuous monitoring of tissue oxygenation may reduce the incidence of such complications by enabling the early detection and correction of tissue hypoperfusion. This approach could lead to more tailored and responsive patient management during and after surgery, potentially improving postoperative outcomes and reducing the overall complication rate associated with off-pump CABG.

Objectives and Endpoints

The following text was from the original protocol registered before the start of the trial.

Primary objective

To establish whether the care guided by cerebral and somatic tissue oxygen saturation monitoring compared to usual care reduces perioperative complications in patients having off-pump coronary artery bypass grafting surgery within 30 days of randomization.

Primary outcome measure

The primary outcome is a collapsed (one or more) composite of the following complications with a Clavien-Dindo grade II or greater arising within 30 days of randomization.

- Brain complications (postoperative delirium, cognition decline, stroke);
- Cardiac complications (non-fatal cardiac arrest, myocardial injury, heart failure, new-onset symptomatic ventricular arrhythmia);
- Respiratory failure;
- Renal complications (AKI stages II and III);
- Infectious complications (surgical site infection involving deep surgical site and/or organ/space, pneumonia, laboratory confirmed bloodstream infection, infection with source uncertain, and sepsis);
- Death.

Secondary objectives

To determine whether the care guided by $SctO_2$ and $SstO_2$ monitoring reduces various complications and duration of hospitalization.

Secondary outcome measures

- Components of the primary composite

- Atrial fibrillation, assessed within postoperative 30 days
- Postoperative delirium assessed from postoperative day 1 to 5
- Postoperative cognitive decline as a continuous variable assessed before surgery and on postoperative days 5 and 30
- Length of hospital stay defined in days from POD 1 to until hospital discharge excluding death

Safety Measures

The following description were based on the original protocol.

Adverse Events (AE)

An AE is any untoward medical occurrence in a subject to whom an intervention has been administered, including occurrences which are not necessarily caused by or related to that intervention. An AE can therefore be any unfavorable and unintended sign, symptom or disease temporarily associated with study activities. However, this study does not involve an investigational medical device, and all trial interventions are already in routine clinical use for patients undergoing a surgical procedure. The safety of the intervention will be monitored by recording acute adverse events at 24 hours and 30 days after randomization as a trial outcome. These events will be monitored at intervals by the DMEC and will be recorded separately as an AE on the CRF.

Serious Adverse Event (SAE)

A serious adverse event (SAE) is defined as an untoward occurrence that:

- results in death
- is life-threatening
- requires hospitalization or prolongation of existing hospitalization significantly beyond normal inpatient stay for the surgery concerned
- results in persistent or significant disability or incapacity

An SAE occurring to a research participant should be reported to the sponsor where in the opinion of the Chief Investigator the event was:

- Related – that is, it resulted from administration of any of the research procedures, and
- Unexpected – that is, the type of event is not listed in the protocol as an expected occurrence.

This study is an investigation of a perioperative intervention. It is expected that patients undergoing major surgery will suffer complications, with consequences up to and including death. Only complications considered by the Chief Investigator to be *related to the use of study procedures* and not a typical surgical complication should be reported as SAEs.

Study Design

The pragmatic trial design selected for the BOTTOMLINE-CS trial is rooted in its focus on evaluating the effectiveness of multisite tissue oxygen saturation monitoring in a real-world clinical setting. This approach emphasizes the applicability of the trial outcomes to typical clinical scenarios by ensuring that the study conditions closely mimic everyday practice. Unlike explanatory trials, which often employ strict participant selection and controlled conditions to determine efficacy under ideal circumstances, a pragmatic trial embraces broader eligibility criteria and diversity in participant characteristics, mirroring the variability seen in daily medical care. Furthermore, the implementation of interventions and monitoring within the usual care processes enables the assessment of the intervention's practical impact, including its feasibility, adherence, and overall utility in routine clinical workflows. The findings from such a pragmatic study are likely to be generalizable and thus informed clinical decision-making.

Sample Size Determination

The following paragraph was from the original protocol registered before the start of the trial. "We assume that the incidence of the composite 30-day complication in the regular care group will be 30% versus 24% in the multisite tissue oxygenation-guided perioperative care group, a 20% relative reduction representing a clinically meaningful and important treatment difference. Based on one-sided Z-test group sequential testing with 3 stages (two interim analyses) and boundary values calculated from O'Brien-Fleming Analog alpha (efficacy) and non-binding beta spending (futility) functions, a total of 927 patients will provide 80% power for detecting a 6% absolute reduction from 30% to 24% at a target alpha-level of 0.05. We plan to recruit 980 patients per group considering a potential ~5% of patients who drop out or have missing data."

Interim Analysis

The following is from the original protocol established before the start of the trial.

"For the interim analyses, O'Brien-Fleming Analog alpha and beta spending functions are used (Table 1, Figure 1). Assuming two interim analyses occur after 33% and 67% of total patients are enrolled and their primary outcome are observed, the nominal alpha levels to reject the null hypothesis for efficacy or fail to reject the null hypothesis for futility are calculated as follows.

Table 1. Critical values and alpha levels for two interim analyses and final analysis

Stage	Target Information (%)	N1	N2	Efficacy Boundary (Critical Z-value scale)	Alpha Spent	Futility Boundary	Beta Spent	Power
1	33%	309	309	±3.710	0.0002		0	-

[figure not shown]
2	67%	618	618	± 2.511	0.0119	± 1.157	0.0828	-
3 (final)	100%	927	927	± 1.932	0.0379	± 1.932	0.1172	0.803

Note: O'Brien-Fleming Analog alpha and beta spending function is adopted

The trial could be stopped for efficacy if the efficacy boundary is crossed at first ($Z < -3.71$, $\alpha < 0.0002$) or second ($Z < -2.51$, $\alpha < 0.0119$) interim analysis, respectively (Figure 1). We will evaluate the combined outcome incidence at the first intermediate analysis and increase sample size at that point if it proves to be lower than anticipated.

If the futility boundary is not crossed ($-1.16 < Z < 1.16$) at second interim analysis, and the study will continue if there is no safety concern. If needed, the sample size of the study might be re-estimated by the DSMB statistician using the observed aggregated data (not the treatment effect) using the conditional power analysis at the interim analysis stage. Since the futility boundary is assumed non-binding, even it is crossed, the DSMB will make recommendation on whether or to stop the trial taking in consideration the totality of accumulated evidence, including the patient accrual rate, observed treatment effect, etc. The whole evaluation will be conducted in a blinded manner.

Figure 1. Group sequential plot

Two interim analyses were performed as per the protocol. No stopping rules were triggered and the DSMB recommended continuing at each analysis. Therefore, the trial proceeded and

finished.

Analysis Populations

Intention-to-Treat (ITT) population: All randomized patients having at least some outcome data will be included in the analysis in the groups to which they were randomized, regardless of the care they received.

Per-Protocol (PP) population: This analysis includes patients, as long as they have outcome data, who completed the study in accordance with the protocol. The patient in the intervention group is determined to have received the intended intervention if their NIRS measurements during the intervention time window are within 90-110% of the baseline value for 80% of the time. The purpose is to assess the effect of the intervention under optimal conditions.

[figure not shown]
Documentation of Deviations:

- All protocol deviations will be documented in a protocol deviation log, which will be reviewed regularly by the trial steering committee to ensure consistency in applying the exclusion criteria.
- The rationale for excluding each participant will be documented in detail.

The primary analyses of the primary and secondary outcomes will be based on the ITT population. The per-protocol population will be used in the safety and sensitivity analysis.

Note: Patients who were randomized and treated, but lost to follow up, will be included to the time of dropout. Patients who withdrew their consent to participate the study will not be included in analysis.

The CONSORT diagram as of January 26, 2024 is presented as follows. The last patient was recruited on December 27, 2023. At the time of formulating this statistical analysis plan, the follow-up per research protocol is ongoing. We anticipated to finish patient follow-up in early February 2024.

We will evaluate the baseline homogeneity using absolute standardized differences. For both primary and secondary analyses, we will correct for baseline factors with ASDs above the threshold determined by the following equation: $1.96 \times \sqrt{(\text{nt} + \text{nc})/(\text{nt} * \text{nc})}$.1 where t is treatment and c is control.

Analysis of the primary outcome

The primary outcome will be evaluated using logistic regression to estimate the odds of postoperative composite complications. A one-sided Z-value < -1.932 will be considered statistically significant.

A sensitivity analysis evaluating an average relative effects model. (Edward J Mascha, Daniel I Sessler. Statistical grand rounds: design and analysis of studies with binary- event composite endpoints: guidelines for anesthesia research. *Anesth Analg*. 2011 Jun;112(6):1461-71. doi: 10.1213/ANE.0b013e31821796d3.)

Analysis of the secondary outcomes

For the secondary analysis of continuous and categorical outcomes in the BOTTOMLINE-CS trial, the following details will outline the statistical methods that will be used. All analyses will be adjusted for unbalanced baseline characteristics and reported with 95% confidence intervals.

- Continuous outcomes will be analyzed using linear regression or generalized linear models as appropriate, depending on the distribution of the data and the study design.
- Composite secondary outcomes will be analyzed using the same approach as the primary outcome.
- Categorical outcomes will be analyzed using logistic regression for binary outcomes or chi-squared tests for categorical variables with more than two categories.
- Bonferroni-Holm's method will be used for multiplicity adjustment for the p values of those secondary outcomes.

Safety analysis

- This analysis will list all adverse events and serious adverse events that were related to the research procedures.
- The analysis will include rows for each type of adverse event and columns for the intervention group, control group, number of events, percentages, and a comparison column if appropriate.

Sensitivity Analysis

Patients who withdrew from the trial voluntarily will not be included in analysis.

In the sensitivity analyses, we will assess the robustness of the trial findings. These analyses deal with the patients who did not have outcome data and the per-protocol population instead of ITT population. The plan for conducting sensitivity analyses in the BOTTOMLINE-CS trial are outlined as follows:

Missing Data:

- In the analyses of the primary and secondary outcomes as detailed above, we will exclude patients without outcome data. This approach corresponds to missing completely at random (MCAR).
- Under the missing at random (MAR) assumption, we will use Markov Chain Monte Carlo (MCMC) for multiple imputation approach with 20 imputed copies. Standard multiple imputation methods will be adopted.
- Under the missing not at random (MNAR) assumption, we will use the following methods.
 - Best-case and worst-case scenario analysis: For binary outcomes, we will impute all missing outcomes as successes in the intervention group and failures in the control group for the best-case scenario and the opposite for the worst-case scenario.
 - Pattern-mixture models: These models will be used to explore the impact of different missing data patterns on the results.
 - Selection models: We will fit models that make specific assumptions about the mechanism of missingness, such as logistic regression models that include a term for whether data are missing or observed.

Analysis based on the per-protocol population

The above specified analyses for the primary and secondary outcomes will be repeated using the per-protocol population.

Reporting of Sensitivity Analyses:

- Results will be reported focusing any changes in significance or the magnitude of the treatment effect compared to the results of the primary analyses specified above.
- A narrative will be provided to explain the implications of the sensitivity analyses findings in the context of the trial conclusions.

Subgroup Analyses

- The outcomes targeted in the subgroup analyses include all primary and secondary outcomes. Interactions between the intervention and primary outcome will be evaluated for each subgroup. Odds ratio for the primary outcome, as a function of subgroup, will be presented as a forest plot with 95% confidence intervals.
- The subgroup analyses will be based on the following variables:
 - Age (< 65 years vs. \geq 65 years)
 - Sex (male vs. female)
 - BMI (< 30 kg/m² vs. $>$ 30 kg/m²)
 - Blood component transfusion during the study period (yes vs. no)
 - Duration of surgery (< 3 hours vs. $>$ 3 hours)
 - Temperature during surgery (based on each patient's median value, $<$ 35.5 °C vs. $>$ 35.5 °C)
 - Cerebral tissue oxygen saturation (based on each patient's median value, $<$ 70% vs. $>/=$ 70%)
 - Somatic tissue oxygen saturation (based on each patient's median value, $<$ 75% vs. $>/=$ 75%)
 - Cardiac output index (based on each patient's median value, $<$ 3 L/min/m² vs. $>/=$ 3 L/min/m²)
 - Systemic vascular resistance (based on each patient's median value, $<$ 1000 dyn·s·cm⁻⁵ vs. $>/=$ 1000 dyn·s·cm⁻⁵)
 - Heart rate (based on each patient's median value, $<$ 60 bpm vs. $>/=$ 60 bpm)
 - Mean arterial pressure (based on each patient's median value, $<$ 65 mmHg vs. $>/=$ 65 mmHg)
 - End-tidal carbon dioxide (based on each patient's median value, $<$ 30 mmHg vs. $>/=$ 30 mmHg)
 - History of stroke (yes vs. no)
 - History of myocardial infarction (yes vs. no)
 - History of hypertension control (based on pre-operative measurement with the threshold of 140/90 mmHg, (yes vs. no)
 - Antihypertensive medication, (yes vs. no)
 - History of diabetes (based on the preoperative diagnosis, yes vs. no)
 - History of chronic renal disease (based on the preoperative diagnosis, yes vs. no)
 - History of chronic obstructive pulmonary disease (based on the preoperative diagnosis, yes vs. no)
 - Current cigarette smoking (yes vs. no)

Ethical Considerations

The ethical considerations were specified in the protocol registered before the start of the trial.

Quality Control and Data Management

The quality control and data management were specified in the protocol registered before the start of the trial.

Software and Programming

R software (version 4.3.2, R Foundation for Statistical Computing, Australia).

Tables and Figures

Creating mock-ups or templates for tables and figures is an essential part of the statistical analysis plan to visualize how the results will be presented. Below are descriptions of the structure and content for the key tables and figures that will typically be included in the results section of a clinical trial report. Please note that actual tables and figures would be created using statistical software and formatted according to the journal or reporting guidelines.

Table 1: Baseline Characteristics of Participants

- This table will present demographic and clinical characteristics of participants at baseline, stratified by treatment groups.
- The table will typically include rows for each characteristic, such as age, sex, BMI, ASA score, comorbidities, and any other relevant baseline measures.
- Columns will be used to display the characteristic's name, the intervention group's data, and the control group's data.
- Standard descriptive statistics will be presented: means and standard deviations for continuous variables; frequencies and percentages for categorical variables. The absolute standardized differences will also be reported.

Table 2: Perioperative Intervention and Relevant Information

- This table will summarize the perioperative interventions, covering both the operative room and intensive care unit periods.
- The table will typically include rows for each intervention or relevant information, such as drugs, fluids, duration of surgery, and mechanical ventilation duration.
- Standard descriptive statistics will be presented: means and standard deviations for

continuous variables; frequencies and percentages for categorical variables. We will report p values depending on the journal style.

Table 3: Primary and Secondary Outcomes Analysis

- This table will summarize the analysis of the primary outcome. Alternatively, and depending on the journal's preference, we can instead present the main results using a forest plot and move the table to supplementary material.
- It will have rows for the outcome measure, the number of events or mean (depending on the nature of the outcome), standard deviation or standard error, and the results of the logistic regression including odds ratios, 95% confidence intervals, and p-values.
- The table will have columns for the intervention group, control group, and the comparison between the two.
- If secondary outcomes are continuous, the table will include mean differences instead of odds ratios.
- Each secondary outcome will be listed with its respective statistical analysis results.
- We plan to move this table to supplementary material as we plan to present the results using a forest plot. The final decision will depend on the journal style.

Table 4: Safety Outcomes

- This table will list all adverse events and serious adverse events reported during the trial. If there are too many AEs to include in the main text, this table will be moved to the supplementary material.
- The table will include rows for each type of adverse event and columns for the intervention group, control group, number of events, percentages, and a comparison column if appropriate.

Figure 1: CONSORT Flow Diagram

- The flow diagram will provide a visual representation of participant flow through the trial, including enrollment, allocation, follow-up, and analysis.
- It will have boxes for each phase and arrows indicating the movement of participants, with numbers for each group at each stage.

Figure 2: Forest plot of the primary and secondary outcomes.

- This figure will present the results of primary and secondary analyses.
- The forest plot will include lines for each subgroup with squares representing the effect estimate (e.g., odds ratio) and horizontal lines representing the 95% confidence intervals.
- A vertical line will represent no effect, and a diamond at the bottom will represent the overall effect size.
- The style of presentation will be similar to the following figure.

[figure not shown]

Figure 3: Forest Plot for Subgroup Analysis

- This figure will present the results of pre-specified subgroup analyses.
- The forest plot will include lines for each subgroup with squares representing the effect estimate (e.g., odds ratio) and horizontal lines representing the 95% confidence intervals.
- A vertical line will represent no effect, and a diamond at the bottom will represent the overall effect size.

Appendices

Inclusion of the SAP approval form, mock tables and figures, and any relevant statistical code.

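### The pre-surgery cognition score enters the cognition model as a covariate only if it is unbalanced by chance; it should be a mandatory covariate

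*SAP*

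**What the plan says.** Under Secondary outcome measures the SAP lists "Postoperative cognitive decline as a continuous variable assessed before surgery and on postoperative days 5 and 30". That gives one pre-surgery score and two follow-up scores per patient.

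The model is given under Analysis of the secondary outcomes: "Continuous outcomes will be analyzed using linear regression or generalized linear models as appropriate, depending on the distribution of the data and the study design". The same section says: "All analyses will be adjusted for unbalanced baseline characteristics and reported with 95% confidence intervals".

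What counts as unbalanced is set in the paragraph just before Analysis of the primary outcome: "we will correct for baseline factors with ASDs above the threshold determined by the following equation". The equation is 1.96 × sqrt((nt + nc)/(nt × nc)), and the rule covers primary and secondary analyses.

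On multiplicity: "Bonferroni-Holm's method will be used for multiplicity adjustment for the p values of those secondary outcomes". On missing outcomes in the main analyses: "we will exclude patients without outcome data".

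The SAP does not name the pre-surgery cognition score as a covariate that is always included. It does not say how decline is computed, or whether the POD 5 and POD 30 results count as one test or two. The instrument and its scoring may stand in the protocol, and their absence here is not the point. The model and the covariate rule are the SAP's own.

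**The concern.** The pre-surgery score is collected on the same scale as the follow-up scores, so it can be expected to explain part of the variation in them. Whether it enters the model is nevertheless left to a balance screen. That screen looks only at the difference between groups at baseline. It takes no account of how strongly a factor predicts the outcome, and the gain in precision comes from that prediction. In most realizations of the trial the score will look balanced and be left out.

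At stake are the width of the confidence interval for cognition and the chance that its p value survives the Holm adjustment. Validity is not at stake: under randomization an unadjusted comparison of difference scores is unbiased, only less precise. A second, smaller gap is that the SAP does not say which visit or visits supply the p values for the Holm procedure.

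**Working it through.** **Inputs.** The visits, model, ASD rule and Holm rule are those quoted above. The SAP states no power, standard deviation, target difference or correlation for cognition, so it has no cognition figure to reproduce. Group sizes come from Sample Size Determination (980 per group recruited) and the table of critical values under Interim Analysis (927 per group at the final stage). As a check that 927 is per group: with the stated boundaries and the stage-2 futility stop applied, 30% versus 24% with 927 per group gives power 0.808 to 0.810, against 0.803 stated.

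**Step 1: the screening threshold.** With equal groups of n the equation becomes 1.96 × sqrt(2/n).
- n = 927: 1.96 × sqrt(2/927) = 0.091
- n = 980: 1.96 × sqrt(2/980) = 0.089

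**Step 2: how often the baseline score passes.** Under randomization the standardized difference of a baseline score has mean 0 and standard error about sqrt(2/n). The threshold is 1.96 of these standard errors, so the score exceeds it with probability 2 × (1 − Φ(1.96)) = 0.05. Assuming the cognition score is among the factors screened, it would be left out about 95% of the time.

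**Step 3: the cost if decline is a difference score.** Take the same variance σ² before and after surgery and correlation rho.
- Difference score: variance 2(1 − rho)σ² per patient.
- Follow-up score adjusted for the pre-surgery score: residual variance (1 − rho²)σ².
- Ratio: 2(1 − rho)/(1 − rho²) = 2/(1 + rho).

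rho is assumed. The last column is 927 × 2/(1 + rho), the number per group that a difference-score analysis needs to match 927 per group analysed with baseline adjustment.

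| rho (assumed) | 2/(1+rho) | Adjusted SE / difference-score SE | Equivalent n per group |
|---|---|---|---|
| 0.4 | 1.43 | 0.837 | 1324 |
| 0.5 | 1.33 | 0.866 | 1236 |
| 0.6 | 1.25 | 0.894 | 1159 |
| 0.7 | 1.18 | 0.922 | 1091 |
| 0.8 | 1.11 | 0.949 | 1030 |

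At rho = 0.9 the factor falls to 2/1.9 = 1.05.

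**Step 4: the same loss as a detectable difference.** For one two-sided 5% test at 80% power, before any Holm adjustment, the detectable difference in SD units is (1.96 + 0.8416) × sqrt(2V/927), with V = 2(1 − rho) or 1 − rho².
- rho = 0.4: 0.143 by difference score, 0.119 adjusted.
- rho = 0.8: 0.082 by difference score, 0.078 adjusted.

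**Step 5: unequal variances.** If the SDs are s0 before and s1 after surgery, the difference-score variance is s0² + s1² − 2·rho·s0·s1 = s1²(1 − rho²) + (s0 − rho·s1)². The first term is the adjusted variance and the second cannot be negative. In a trial of this size, adjustment therefore does not lose precision. It breaks even only if the regression slope of follow-up on baseline is exactly 1.

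**The case against.** The strongest reply is that the SAP does not commit itself to an inefficient analysis. Regressing the follow-up score on group and pre-surgery score is itself linear regression, so the named method allows it. Decline is never defined as a difference, and the clause tying the model to the data distribution and study design leaves latitude. If the score did pass the ASD screen, a difference-score regression with that covariate would give the same group effect as modelling the follow-up score given baseline. All of this stands. It means the loss is conditional, and the SAP leaves the choice open. It does not supply the missing prespecification, because the only stated route into the model is the balance screen.

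A reader might go further and infer three things that the SAP does not support.
- **That one response per patient forces the baseline to enter by subtraction.** It does not, since a single-response regression can carry any covariate.
- **That the two visits will be stacked as independent rows in one regression, or that two correlated cognition tests invalidate the Holm procedure.** Nothing in the SAP proposes stacking, and Holm controls the familywise error under any dependence.
- **That only a repeated-measures model recovers the lost precision.** With complete data, such a model with unstructured covariance and visit-specific baseline effects gives the same POD 5 and POD 30 estimates as separate baseline-adjusted regressions. It adds information only for a pooled effect or when a visit is missing.

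It can also be said that the stakes are low: this is one secondary outcome, and the loss is small if rho is high. That is correct.

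**Conclusion.** The point holds as a gap in prespecification with a likely loss of precision. Under the ASD rule the pre-surgery cognition score would be a covariate only about 5% of the time. If decline is analysed as a difference score, the variance of the group difference is then 1.43 to 1.11 times what the same data allow, for rho from 0.4 to 0.8.

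The size rests on three assumptions: the value of rho, equal variances at the two times, and decline taken as a difference. The SAP gives none of them, so this is a range and not a figure of the trial. It is a worthwhile minor improvement. It does not touch the primary analysis, and it does not show that the SAP's cognition comparison would be invalid.

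**What to change.** In Analysis of the secondary outcomes, add for cognition:
- The pre-surgery score is a covariate in the model at each visit, whatever its ASD. The imbalance rule continues to apply to other factors.
- The adjusted group difference is reported at POD 5 and at POD 30, each with a 95% confidence interval.
- The visit or visits whose p values enter the Holm family are named.

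Optionally, fit both visits in one repeated-measures model with unstructured within-patient covariance and baseline effects by visit. The reason would be to retain patients with only one follow-up score, whom a single-visit regression drops at the missing visit. It is not needed for the precision gain shown above.

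The cost is a few lines of SAP text and a standard model in R, using a score already collected. The small downside is that the estimate becomes a baseline-adjusted score difference and no longer a raw mean decline; raw decline can still be tabulated by group.

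### Length of stay is compared only among patients discharged alive, so a tested secondary outcome conditions on an event that occurs after randomization

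*SAP*

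**What the plan says.** The secondary objective in the SAP is to find out whether guided care "reduces various complications and duration of hospitalization". The outcome that serves the second half of that aim, under Secondary outcome measures, is "Length of hospital stay defined in days from POD 1 to until hospital discharge excluding death".

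Four other statements decide how it will be analysed:

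- Analysis of the secondary outcomes: "Continuous outcomes will be analyzed using linear regression or generalized linear models as appropriate". The same section puts the p values of the secondary outcomes under a Bonferroni-Holm adjustment, so length of stay is a tested outcome.
- Sensitivity Analysis, Missing Data: "In the analyses of the primary and secondary outcomes as detailed above, we will exclude patients without outcome data".
- Analysis Populations: "The primary analyses of the primary and secondary outcomes will be based on the ITT population". That population is defined by "All randomized patients having at least some outcome data will be included in the analysis in the groups to which they were randomized".
- Primary outcome measure: "The primary outcome is a collapsed (one or more) composite of the following complications with a Clavien-Dindo grade II or greater". Death within 30 days of randomization is the last item on that list, and it is a secondary outcome in its own right through "Components of the primary composite".

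The SAP contains no length-of-stay analysis in which death is a competing event, is ranked as the worst result, or is counted against days out of hospital.

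**The concern.** Randomization makes the arms comparable at baseline. It does not make those who later leave hospital alive comparable, because the intervention may affect who they are. Suppose guided care saves some patients who would have died under usual care. These are likely to be among the sickest, with long stays, and they enter the mean of the intervention arm while their counterparts are absent from the control mean. Guided care then appears to lengthen stay although nobody's stay was lengthened. The reverse also holds: an arm with more deaths loses its sickest patients from the average and can appear to shorten stay.

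What is at stake is the reading of one Holm-tested secondary result that answers a named objective. The error, where there is one, favours the arm with more deaths.

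**Working it through.** **Step 1. Who is in the comparison?** The closing words of the definition can be read in two ways.

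- *Reading A:* patients who die are removed from this outcome.
- *Reading B:* death does not count as discharge.

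Under B, a patient who dies in hospital never has a discharge date, so has no value for a linear or generalized linear model, and the missing-data rule drops that patient. In-hospital deaths leave the comparison on either reading. The readings differ only for a patient who goes home and dies later: B keeps that patient, while A may not. What is certain is that the comparison is restricted to patients discharged alive.

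**Step 2. Does another part of the SAP repair this?** The best-case and worst-case imputation is stated for binary outcomes only. Multiple imputation, pattern-mixture and selection models are listed for missing data and do not mention death. If deaths were passed to the multiple imputation as missing, it would invent discharge days for patients who were never discharged.

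**Step 3. How large could the shift be?** The SAP gives no death rate, mean stay or SD, so there is no figure to reproduce. The following is an illustration.

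Inputs:

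- 927 patients per arm: SAP, Interim Analysis, Table 1, final stage (used for scale only).
- Death risks dC (control) and dT (intervention): assumed.
- E, the extra days that the saved patients stay compared with other survivors: assumed 5 to 20.
- Also assumed: the intervention changes nobody's stay, and nobody dies under it who would have survived usual care.

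In the intervention arm a fraction 1 − dC would survive in either arm, with mean stay m. A fraction dC − dT is saved, with mean m + E. The mean among its survivors is m + E × (dC − dT)/(1 − dT). The control survivors have mean m. So

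spurious difference = E × (dC − dT)/(1 − dT).

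| dC | dT | Deaths per 927 (control vs intervention) | (dC − dT)/(1 − dT) | E = 5 days | E = 20 days |
|---|---|---|---|---|---|
| 2% | 1.6% | 18.5 vs 14.8 | 0.004/0.984 = 0.0041 | 0.02 day | 0.08 day |
| 1% | 0.5% | 9.3 vs 4.6 | 0.005/0.995 = 0.0050 | 0.03 day | 0.10 day |
| 2% | 1% | 18.5 vs 9.3 | 0.010/0.990 = 0.0101 | 0.05 day | 0.20 day |
| 3% | 1.5% | 27.8 vs 13.9 | 0.015/0.985 = 0.0152 | 0.08 day | 0.30 day |
| 3% | 3% | 27.8 vs 27.8 | 0 | 0 | 0 |

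The first row applies the 20% relative reduction that Sample Size Determination assumes for the composite. The next three halve mortality, which is a large effect. The last row is zero because, in this model, equal risks mean that the same patients die in either arm. If the intervention raises mortality, exchange the arms and the sign reverses.

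**Step 4. Against sampling error.** With an assumed SD of 5 to 8 days, the standard error of a difference in means is SD × √(2/927) = SD × 0.0464, or 0.23 to 0.37 day. The first row is at most 0.08/0.23 = 0.35 of a standard error. The largest entry, 0.30 day, is 0.8 to 1.3 standard errors.

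**The case against.** The strongest reply has four parts.

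- *The exclusion is deliberate and has a reason.* It stops an early death from counting as a short stay, which would be a worse artefact. This stands, and it is why the registered comparison should be kept.
- *It does not breach intention to treat.* A reader might infer a contradiction, because secondary outcomes are assigned to the ITT population and a patient who died has outcome data. The SAP does not support that reading. Patients who die stay in the ITT population, in their randomized arm, and count in the composite and its death component. For this one outcome they have no value, by an explicit endpoint definition. The weakness is that the definition makes the comparison conditional and the SAP does not say so.
- *Deaths will be visible.* Death is reported by arm as a component, in the same table or forest plot as length of stay, so a reader could notice an imbalance. This largely stands. However, the component counts deaths within 30 days of randomization, whereas the patients lost from this comparison are those who die in hospital. Visibility also does not correct the estimate.
- *The effect is small and every input is assumed.* This stands. The effect also works against an intervention that prevents deaths, so in that case it is conservative.

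The outcomes are quoted from the registered protocol, and the SAP was written after the last patient had been recruited. That argues against replacing the registered analysis, but not against adding one beside it.

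**Conclusion.** The point holds in limited form. As specified, length of stay is compared among patients discharged alive, and no other part of the SAP accounts for those who die in hospital. The bias arises only if mortality differs by arm, or different patients die in each, and those affected would have had stays unlike the rest. If they would have stayed longer, the arm with more deaths is favoured.

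The size is about 0.02 to 0.3 day under 1–3% control mortality, relative reductions of 20% to 50%, and 5 to 20 excess days. All of these are assumptions.

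Two stronger readings should be avoided. One is that everyone who dies is excluded: the wording leaves open whether a patient who dies after discharge is kept. The other is that the Holm-tested result is likely to be reversed: most of the illustrated shifts are below one standard error, and no figure in the SAP shows a mortality difference large enough to do it. This is a minor improvement to one secondary outcome.

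**What to change.** In the SAP, under Secondary outcome measures and Analysis of the secondary outcomes:

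1. Add an analysis of all randomized patients, in their allocated arms, of time from POD 1 to discharge alive, with in-hospital death as a competing event. Patients who die in hospital are never counted as discharged. A subdistribution (Fine-Gray) model with cumulative incidence curves of live discharge does this. Merely censoring at death would not.
2. Keep the registered comparison, but label it as conditional on discharge alive and state whether patients who die after discharge are included.
3. Report in-hospital deaths by arm beside it.
4. Base any claim of shorter stay on agreement of the two analyses, and define agreement beforehand. Because both must agree, the extra analysis does not raise the false-positive rate.

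The cost is one extra model, which needs only discharge and death dates. The downside is that its effect is on a discharge-rate scale, which is harder to explain than a difference in mean days. The registered analysis still supplies that difference.
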